3.1.4.3 Missing items in scales and subscales

The number (%) with complete primary and secondary outcome data will be reported by trial arm and assessment time point and overall.

Where the primary publication for a questionnaire does not give instructions for how to deal with missing data, the total pro-rata score will be calculated provided that the level of missingness at the item level is less than 20%. In this way, the total score will be calculated provided that at least, for example, five out of six items are present. If five items are non-missing, the mean of these five will be used to impute the sixth. Where guidance is available it is detailed in Appendix 1 for a questionnaire.

3.1.4.4 Missing baseline data

There should be little missing baseline data as it should generally be complete prior to randomisation. Where there is missing baseline viral load, PHQ-9, self-report adherence, or pharmacy refill adherence data, simple mean imputation will be used to impute those data (White and Thompson) prior to any further coding/dichotomisation of variables as follows: viral load – viral copies/mL, PHQ-9 – the total score, self-report adherence the total score, pharmacy refill – the percentage adherence.

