3.1.1 Analysis of primary outcome

The viral load data will be coded into a binary variable as follows: <1000 copies/mL (suppressed) or ≥1000 copies/mL (not suppressed), please also see Appendix 1. Where the viral load data are missing at 12 months and the individual has died, the data will be left missing unless it is apparent from medical or death records that the person died due to high viral load or death was clearly AIDS related, in which case we will code them as not suppressed. The odds ratio at 12 months (and associated 95% CI) for <1000 copies/mL for TENDAI vs EUC will be estimated using a logistic regression model with the 12 month measure as the dependent variable, and trial arm as the independent variable, as well as the site stratification variable. We will fit two models, the one just described excluding baseline log viral load, and another including this as an independent variable, so will present odds ratio estimates both marginal and conditional with respect to baseline viral load. Moderation of treatment effects by sex will be assessed in these two final model backgrounds as outlined in Section 3.1.3.

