3.1.2 Analysis of secondary outcomes

The mean difference at 12 months (and associated 95% CI) in PHQ-9 between TENDAI and EUC, and a standardised effect size, will be estimated using a linear mixed effects model with the 4, 8 and 12 month measures as dependent variables; a random intercept at the participant level, with a random slope if warranted (assessed via likelihood ratio test); baseline PHQ-9, trial arm, time, and trial arm by time interaction terms as independent variables; as well as the site stratification variable. Note for this PHQ-9 outcome that while we will include all post-randomisation measures as dependent variables in the model in order to account for missing data, we will not present treatment difference estimates for 4 and 8 months (as per the trial objectives/outcomes).

Pharmacy refill data will be recoded into a binary variable: greater than or equal to 90% adherence in the past month or less than 90% adherence in the past month. Please refer to Appendix 1 – Scoring of outcome measures. The odds ratio at 4, 8 and 12 months (and associated 95% CI) for ≥90% pharmacy refill adherence between TENDAI and EUC will be estimated using a logistic mixed effects model with the 4, 8 and 12 month measures as dependent variables with a random intercept at the participant level, consideration of a random slope variable and similar independent variables as those described for PHQ-9. Please see the end of the section for some further details on the modelling of this binary variable.

Self-report adherence (Wilson et al) will be scored as described in the paper and modelled as described for PHQ-9.

The mean difference in log copies/mL of viral load at 12 months (and associated 95% CI) between TENDAI and EUC will be estimated using a linear regression model with the log viral load at 12 months as the dependent variable,

baseline log viral load and trial arm as independent variables, as well as the site stratification variable. Undetectable viral loads will be set to half the viral detection load limit of the Marondera Provincial Hospital lab machine, which is 15.

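### Missing baseline viral load is averaged in copies/mL but used on the log scale, so imputed values sit above the covariate's centre; impute on the scale the model uses

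*SAP*

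**What the plan says.** SAP 3.1.4.4 covers missing baseline viral load, PHQ-9, self-report adherence and pharmacy refill: "simple mean imputation will be used to impute those data (White and Thompson) prior to any further coding/dichotomisation of variables as follows: viral load". The scales it names include "viral load – viral copies/mL" and "pharmacy refill – the percentage adherence". It expects few cases: "There should be little missing baseline data as it should generally be complete prior to randomisation".

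The models use other scales:

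- **Primary outcome (SAP 3.1.1).** Two logistic models are fitted, one "excluding baseline log viral load, and another including this as an independent variable".
- **Log viral load (SAP 3.1.2).** The linear regression has "baseline log viral load and trial arm as independent variables, as well as the site stratification variable".
- **Refill (SAP 3.1.2).** For the outcome, "Pharmacy refill data will be recoded into a binary variable: greater than or equal to 90% adherence in the past month" or below it. The covariates are described only as similar to those of the PHQ-9 model. SAP 3.1 says an outcome that is also recorded at baseline will generally be a covariate. Neither section says whether baseline refill enters as the indicator or as the percentage.

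PHQ-9 and self-report adherence are imputed as total scores, which is the form in which they are modelled.

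**The concern.** Single mean imputation of a baseline covariate puts the patient at the centre of that covariate only if the mean is taken on the scale that enters the model. Viral load is right-skewed, so its arithmetic mean is pulled up by the largest values. After the log is taken, the imputed patient is no longer average but has a fairly high viral load.

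For refill, imputing a percentage and then cutting at 90% gives every imputed patient the same code. The mean of the 0/1 indicator would be neutral.

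At stake are the covariate values of any patient with a missing baseline value and, through them, a little of the precision that baseline adjustment is meant to add.

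**Working it through.** SAP 3.1.4.4 states no figure, so there is none to reproduce.

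**1. Direction.** By Jensen's inequality, log10(mean of VL) is at least the mean of log10(VL). This needs no outside figure.

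**2. Size for viral load.** Input from the documents: entry viral load is above 1000 copies/mL, i.e. above 3 log10 (SAP 1.3.1). Assumed, because the documents do not give them: a normal distribution of log10 viral load, its mean and its SD.

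Without truncation, gap = SD² × ln(10)/2. At SD 0.5 this is 0.25 × 2.303/2 = 0.29. At SD 1.0 it is 1.15. The table restricts values to 3–7 log10, with an underlying mean of 4.0 to 5.0.

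| Underlying SD | Gap, log10 |
|---|---|
| 0.5 | 0.27–0.29 |
| 0.6 | 0.37–0.41 |
| 0.8 | 0.61–0.65 |
| 1.0 | 0.75–0.83 |

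An underlying mean of 3.5 gives 0.21, 0.29, 0.51 and 0.75 at the same four SDs. As an example in SD units, mean 4.3 and SD 0.8 give a gap of 0.64 against a truncated SD of 0.72, so 0.64/0.72 = 0.89 SD.

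**3. Refill, if the covariate is binary.** The documents give no baseline refill distribution. Three assumed ones:

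- 40% at full refill, the rest uniform on 0–90: 40 + 0.6 × 45 = 67%. All imputed patients are coded below 90%.
- 60% at full refill, the rest uniform on 30–90: 60 + 0.4 × 60 = 84%. All are coded below 90%.
- 80% at full refill, the rest uniform on 50–90: 80 + 0.2 × 70 = 94%. All are coded at or above 90%.

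Imputed patients always share one class; which class depends on the observed mean.

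**4. Precision in the linear log viral load model.** Let p be the missing fraction (missing at random with respect to everything else), d the offset of the imputed value in SDs and r the baseline-outcome correlation. Explained variance falls from (1−p)r² with log-scale imputation to (1−p)r²/(1+pd²). Take d = 0.95.

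- p = 5%, r = 0.5: 0.2375 falls to 0.2375/1.045 = 0.2272. The variance ratio is 0.7728/0.7625 = 1.0134, so the SE rises 0.67%.
- p = 5%, r = 0.3: 0.0855 falls to 0.0818. The ratio is 1.0040, so the SE rises 0.20%.
- p = 2%: SE up 0.09–0.29% for r = 0.3–0.5. p = 1%: 0.04–0.15%.
- At r = 0.6 and p = 5% the rise reaches 1.1%.

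A simulation agrees (n = 290, 3,000 runs, true effect −0.60, baseline mean 4.3 and SD 0.8 restricted to above 3, slope 0.5, residual SD 1.2):

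| Missing | Estimate, raw mean | Estimate, log mean | SE, raw mean | SE, log mean |
|---|---|---|---|---|
| 5% | −0.602 | −0.602 | 0.1417 | 0.1414 |
| 20% | −0.600 | −0.600 | 0.1429 | 0.1422 |

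**5. Logistic primary model.** A simulation used 232 patients (290 × 0.8), about 45% versus 65% suppressed, an assumed slope of −0.8 log-odds per SD and an imputed value 0.95 SD too high. With 5% missing, going from mean-centred to raw-mean imputation moved the log odds ratio from 0.9615 to 0.9565 and the SE from 0.2934 to 0.2925. Power moved from 91.3% to 91.2%. With 10% missing, power moved from 91.0% to 90.7%.

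**The case against.** The strongest reply is that the rule will hardly ever be used. A viral load above 1000 copies/mL is an entry criterion. Protocol section 8 has the viral load result confirmed as received before randomisation. Section 13 requires staff to complete all baseline data first, and section 18b says people who do not finish baseline are not randomised. Pharmacy refill is on the baseline list in section 18a, so the same safeguards cover it. One of the two primary models omits baseline viral load altogether. All of this stands, and it makes this a minor point. The 5% to 20% missing rates above are stress tests, not forecasts.

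Four stronger readings are tempting, and the documents do not support them:

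- **Imputed patients are always coded non-adherent.** That needs an observed mean refill below 90%, which is plausible in a viraemic sample but not given. If 65% refill fully and the rest average 75%, the mean is 65 + 0.35 × 75 = 91.25%, and all are coded adherent. It also needs the covariate to be binary, which the SAP leaves open.
- **The excess is 0.6 to 0.8 log10.** This needs a particular SD, and the documents give none.
- **All the adjusted models lose precision.** The percentages in step 4 apply to the linear model only. In the logistic simulation the SE fell slightly.
- **The screen for predictors of missing data is distorted.** SAP 3.1.4.5 lists baseline viral load there without a scale. If copies/mL is screened, the raw mean is the neutral value.

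**Conclusion.** The point holds as a small, free improvement. It is certain from the text that viral load is averaged on one scale and used on another, and that the imputed value therefore lies above the mean log10. The size, about 0.3 to 0.8 log10, rests on assumed SDs of 0.5 to 1.0 with values above 1000 copies/mL. The refill part is conditional on binary entry.

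A reader might infer that the treatment comparison is biased. It is not in the linear model, because the imputed value does not depend on arm. In the logistic simulation the log odds ratio moved by only 0.005, about 0.5% of its value. The SE of the linear log viral load model rises from under 0.1% to about 0.7% at 1% to 5% missing, assuming a baseline-outcome correlation of 0.3 to 0.5. Few values should be missing, so no conclusion of the trial is likely to turn on this.

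**What to change.** In SAP 3.1.4.4, impute on the scale used in the model:

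- **Viral load:** the mean of log10 baseline viral load across both arms, replacing the mean of copies/mL.
- **Refill:** state in SAP 3.1.2 how baseline refill enters. If it is the 90% indicator, impute its overall proportion across both arms. If it is the percentage, keep the mean percentage.
- **PHQ-9 and self-report adherence:** no change.

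This costs a sentence or two in the SAP and needs no extra data or analysis. If no baseline values turn out to be missing, it changes nothing. It is best settled before analysis, because the trial statistician is unblinded (SAP 3.1) and a later change of rule could look post hoc.

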3.1.4.5 Missing outcome data

Where there are repeated post-randomisation outcome measures, missing outcome assessments will be dealt with by fitting appropriate models to all the available data using maximum likelihood methods or quasi-likelihood methods (Generalized Linear Mixed models). Such an approach provides valid inferences under the assumption that the missing data mechanism is ignorable (or MAR), i.e. all predictors of missing data are included. We will seek baseline predictors of missing data and include them as per Section 3.1. Also as mentioned in Section 3.1, we will only consider multiple imputation (MI) if post randomisation variables are found to be predictive of missing viral load outcome data (Sullivan et al), so we will assess a few pre-specified post-randomisation variables to see if they predict missing outcome data.

Baseline variables predictive of missing viral load data at 12 months.

A binary variable coding whether any primary or secondary outcomes are missing at any time point will be prepared and used as the dependent variable in a logistic regression model. The independent variables in the logistic regression model will be trial arm, site and the baseline covariate under investigation. This will be repeated for each of the baseline variables of interest. The following baseline variables will be tested as they are thought to be likely predictors of missing viral load data at 12 months: age, relationship status, education level (recoded as a single variable), income (recoded as a single variable), baseline self-report adherence to ART, baseline viral load, baseline PHQ-9 depression, access to mobile phone. Recoding of variables is described in Appendix 1 scoring of outcome measures. Each variable will be considered to predict missing viral load data if there is a significant relationship at a 5% level.

Post-randomisation variables predictive of missing viral load data at 12 months.

This will be assessed in a similar way to that used to identify which baseline variables predict missing outcome data. We will assess whether completion of therapy (in the TENDAI arm only) and self-report ART adherence at 12 months are predictive of missing data.

If there are post-randomisation variables that predict missing outcome data, we will impute a number of datasets equal to the percentage missing data in the primary viral load outcome (Dong and Peng) or 50 datasets (whichever is higher). As well as the relevant variables from Sections 3.1.1 and 3.1.2, the imputation model will include all baseline and post-randomisation variables we find to predict missing outcome data and the putative moderating variable sex, imputing the trial arms separately as recommended by Thomas et al when moderation analysis is planned. We will endeavour to construct the imputation models as described, but if not viable, we may need to consider a set of simpler imputation models (i.e. when imputing with interaction terms we may need to remove some other variables from the imputation model). Where MI is used, we will produce estimates from both the complete case and MI data and include both in the statistical report, with the latter being the main estimates reported in the primary publication. If there are no post-randomisation variables that predict missing outcome data, but there are baseline variables predictive of missing data, these will be included in the non-logistic primary and secondary outcome analysis models (i.e. PHQ-9, self-report adherence, log viral load).

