3.1.5.2 COVID19

We will describe the baseline characteristics of participants as described in Section 2.2 also split by randomisation date before and after the pandemic started on 30th March 2020. We will also describe the baseline measures of the primary and secondary outcomes split by randomisation date before and after the pandemic started. We will summarise post-randomisation measures of the primary and secondary outcomes as described in Section 2.7 also split by collected before and after the pandemic started on 30th March 2020.

We do not expect that between group differences would be altered by COVID, but we will perform the following analysis to explore this. As the pandemic has progressed somewhat differently in Zimbabwe as compared to the UK, with different periods of lockdown, the study team have been keeping track of key dates and we expect to be able to construct a variable of this sort: 1 = pre-COVID, 2 = key post COVID period 1, key post COVID period 2, etc. These key periods should align with events like start and stop of lockdowns, curfews and changes to local transport. We will then perform an analysis on the primary binary viral load outcome and the secondary log viral load outcome where we add a trial arm by COVID period interaction term. If an omnibus test across the interaction term parameters is significant at $p < 0.05$, we will report between group differences in these two variables separately for the different time periods.

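### If viral load is multiply imputed, leaving COVID period out of the imputation model pulls the planned arm-by-COVID-period interaction towards zero

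*SAP*

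**What the plan says.** SAP 3.1 and 3.1.4.5 make multiple imputation conditional. It is considered only if at least 10% of outcome data are missing and a post-randomisation variable predicts missingness. Where it is used, complete-case and imputed estimates both go in the statistical report, "with the latter being the main estimates reported in the primary publication".

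The imputation model has three sources: the relevant variables of 3.1.1 and 3.1.2, whatever is found to predict missingness, and sex ("the imputation model will include all baseline and post-randomisation variables we find to predict missing outcome data and the putative moderating variable sex"). The arms are imputed separately, and the stated reason is the planned moderation analysis.

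SAP 3.1.5.2 describes an exploratory analysis of binary suppression and log viral load, "where we add a trial arm by COVID period interaction term". Period-specific differences are reported only if the omnibus test gives p < 0.05. The SAP does not say whether this analysis uses imputed or complete-case data. Nor does it say which date assigns a participant's period: baseline summaries are split by randomisation date, while outcome summaries are "also split by collected before and after the pandemic started on 30th March 2020".

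**The concern.** An imputation model should contain any effect modifier that will later be tested. Otherwise the imputed values are drawn as if the modifier had no effect, and they dilute the interaction. The SAP accepts this principle for sex and does not carry it over to COVID period, the other planned arm interaction on the primary outcome.

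The dilution is towards no difference between periods, which is the result that 3.1.5.2 says it expects. Because period-specific effects appear only after a significant omnibus test, a diluted interaction could also keep them out of the report.

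**Working it through.** **The plan's own figure.** SAP 1.9 gives 85% power for 45% v 65% with 290 randomised and 20% attrition. With 290 × 0.8 / 2 = 116 per arm, exact enumeration of the two-sided Fisher test at 5% gives 85.0%, so it reproduces. The SAP gives no figure for the COVID interaction.

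**Does any rule bring period in?**
- Primary model (3.1.1): "trial arm as the independent variable, as well as the site stratification variable", fitted with and without baseline log viral load. No period.
- Secondary models (3.1.2): baseline value, arm, site and, for repeated outcomes, follow-up time and its interaction with arm. Time there is the visit, not calendar period.
- Baseline candidates for predicting missingness (3.1.4.5): "age, relationship status, education level (recoded as a single variable), income (recoded as a single variable), baseline self-report adherence to ART", then baseline viral load, PHQ-9 and mobile phone access. No period.
- Post-randomisation candidates: whether "completion of therapy (in the TENDAI arm only) and self-report ART adherence at 12 months are predictive of missing data". No period.
- Named moderator: sex only.

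Site is in the imputation model; COVID period is not.

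**Shrinkage when nothing stands in for period.** Let p be the true suppression rate in one arm and period, p̄ the arm average and m the share missing, with missingness unrelated to outcome within arm and period. Imputing by arm without period gives an expected rate of

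q = (1 − m)p + m·p̄.

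The gap between periods within an arm, and so the interaction on the risk-difference scale, is multiplied by (1 − m).

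Assumed rates: two equal periods; EUC 45% in both; TENDAI 75% and 55%, which average the planned 65%. The true interaction is 20 points (log odds ratio 0.898 in absolute value).
- m = 10%: TENDAI becomes 0.9 × 75 + 0.1 × 65 = 74.0% and 0.9 × 55 + 0.1 × 65 = 56.0%. The interaction is 18 points (90% kept); log odds ratio 0.805 (89.6% kept).
- m = 20%: TENDAI becomes 73.0% and 57.0%. The interaction is 16 points (80% kept); log odds ratio 0.713 (79.4% kept).
- 20% missing on average but unequal by period (10%/30% or 5%/35%): 79% and 77% kept on the risk-difference scale.

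**Allowing for site.** The second site was added later (SAP amendment table, entry of 23/03/2022), so site partly stands in for calendar time. Suppose earlier participants all come from the first site, a share s of later participants come from the second, and site has no effect of its own. The imputed values then keep s/(2 − s) of the period gap, so the shrinkage is m × [1 − s/(2 − s)].

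For s = 0.5 in the TENDAI arm:
- First-site mean: (0.5 × 75 + 0.25 × 55) / 0.75 = 68.3%. Second-site mean: 55%.
- Imputed early rate 68.3%; imputed late rate (68.3 + 55)/2 = 61.7%; imputed gap 6.7 points, one third of 20.
- At m = 20%: 0.8 × 20 + 0.2 × 6.7 = 17.3 points, which is 13% smaller than the truth.
- At m = 10% the same formula gives 0.10 × (1 − 1/3) = 6.7%.

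For s = 0.3 and 0.7 at m = 20% the shrinkage is 16% and 9%. The documents do not give s.

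**Simulation.** Same assumed rates, logistic imputation by arm on baseline viral load, sex and self-report adherence, no site term. In large samples the ratio of the imputed-data interaction to the full-data interaction was:
- period omitted: 0.90 at 10% missing, 0.80 at 20%;
- period omitted, with adherence shifted by an assumed 1 SD with outcome: 0.91 and 0.83;
- period included: 1.00 to 1.01 throughout.

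Power of the interaction test at n = 290 (1,500 runs, 50 imputations):

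| Missing | Imputation model | Complete case | Imputed |
|---|---|---|---|
| 10% | period omitted | 42% | 35% |
| 10% | period included | 41% | 41% |
| 20% | period omitted | 39% | 22% |
| 20% | period included | 36% | 36% |

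Each row is a separate set of runs, so the complete-case column differs between rows by simulation error.

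**The case against.** The strongest reply is that several conditions must all hold: at least 10% missing, a post-randomisation predictor of missingness, and a COVID analysis run on imputed data, which 3.1.5.2 never says. Protocol 20c expects attrition well under 20%. Complete-case estimates are reported beside imputed ones, and if that rule covers 3.1.5.2 an undiluted interaction would be on file. The analysis is exploratory and weak in any case: with 39% power or less at 20% missing in the assumed scenario, a null result says little with or without period in the model. With about 145 participants per arm and an open number of periods, adding period could also produce sparse cells. All of this stands, and it limits the importance of the point. It does not remove the gap, because the SAP's list taken as written omits period and the SAP is silent on which data the test uses.

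A reader might infer three stronger things that the documents do not support:
- **That imputation always shrinks the interaction by the share missing.** That is roughly a ceiling. Site enters through 3.1.1 and partly tracks calendar period, and auxiliary variables can carry outcome information.
- **That the primary treatment comparison is biased.** This route affects only the contrast between periods, not the overall difference between arms.
- **That a period based on outcome date cannot be used in imputation because participants without a result have no collection date.** SAP 1.7 works from an expected visit date, which follows from randomisation and exists for everyone.

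**Conclusion.** The point holds as a conditional one. When imputation is triggered and the 3.1.5.2 test is run on imputed data, the 3.1.4.5 model biases the arm-by-COVID-period interaction towards zero. The loss is at most about 10% at 10% missing and about 20% at 20% missing; it is about 13% at 20% missing if half of later participants come from the second site. In the assumed scenario without site, power at 20% missing falls from 39% (complete case) to 22%.

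These figures rest on assumed period rates, two equal periods and an assumed site mix. The direction, and the approximate ceiling at the share missing, follow from the formula under missingness unrelated to outcome within arm and period. The consequence is modest: a low-powered exploratory check is weakened further in the direction the SAP expects. The correction is cheap enough to be worth making before unblinded analysis.

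**What to change.** In SAP 3.1.4.5, add COVID period to the by-arm imputation model alongside sex, with sparse periods merged by a rule fixed in advance. Alternatively, state in 3.1.5.2 that the arm-by-period interaction is estimated on complete cases.

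In either case, 3.1.5.2 should assign period by one date known for every participant: the randomisation date or the expected 12-month visit date. The two answer different questions. The first reflects conditions at entry; the second reflects conditions about when the outcome was due. The team should choose one and use it for observed and missing outcomes alike.

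The cost is a sentence or two in the SAP and one more categorical variable in the imputation model, with possible sparse cells. SAP 3.1.4.5 already allows simpler imputation models if the full one is not viable. The complete-case option avoids the sparse cells but gives up what imputation was meant to add for this test.
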